### **13.2 BETTER-B Operational Definitions**

Adverse events will be collected for all participants and will be evaluated for intensity and causal relationship with the trial medication or other factors according to the National Cancer Institute (NCI) CTCAE V4.0 (NCI-CTCAE). A copy is provided in the BETTER-B Investigator Site File and may also be obtained at:

http://ctep.cancer.gov/protocolDevelopment/electronic\_applications/ctc.htm

Published date: May 28, 2009

#### 13.2.1 Adverse Events (AEs) / Adverse Reactions (ARs) and Serious Adverse Events (SAEs) / Serious Adverse Reactions (SARs)

For general definitions of AEs, ARs, SAEs and SARs, please see section 13.1 above.

As this is a blinded trial, all AEs and SAEs should be assessed for causal relationship assuming that the participant has been receiving mirtazapine.

Routinely breaking the blind could compromise the integrity of the trial. For this reason blindbreaking will only take place where information about the participant's trial treatment is clearly necessary for the appropriate medical management of the participant. In all cases the Investigator would be expected to evaluate the causality of AEs or SAEs as though the participant was receiving the active medication.

When determining whether a SAE or SAR is expected or not, please refer to the pharmacovigilance reference copy of the mirtazapine Summary of Product Characteristics (SPC) (Medreich Plc; PL number 21880/0053).

#### Events not to be classed as SAEs on this BETTER-B Feasibility trial

The following events will not be classed as SAEs within this trial and will therefore not be subject to expedited reporting (they will still need to be reported to CTRU along with other AEs):

Hospitalisation or admission into a hospice, nursing home or palliative care unit due to:

- Care-giver burden;
- Expected deterioration related to underlying cancer diagnosis;
- Expected deterioration related to underlying lung disease diagnosis (COPD / ILD);
- Expected deterioration related to underlying chronic heart failure diagnosis (e.g. acute decompensation of heart failure, angina with or without raised troponins, cardiac arrhythmia Routine treatment or monitoring of the studied indication not associated with any deterioration in condition;

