## 8.2 Exclusion Criteria

- 1. Existing antidepressant useiii, use of linezolid, or St John's wort
- 2. Known contraindication to mirtazapineiv
- 3. Hypersensitivity to the active substance or to any of the components of the mirtazapine or placebo (e.g. lactose intolerance)
- 4. Australia modified Karnofsky Performance Scale ≤40v
- 5. Pregnant or breast-feeding women vi
- 6. Patients with acute cardiac events within 3 months of randomisation (myocardial infarction, unstable angina pectoris, or significant cardiac conduction disturbance)
- 7. Patients with known hepatic impairment
- 8. Patients with known renal impairment
- 9. Patients with uncontrolled blood pressure
- 10. Patients with uncontrolled diabetes mellitus
- 11. Patients with uncontrolled seizures, epilepsy or organic brain syndrome
- 12. Patients with severe depression or suicidal thoughts
- 13. Patients with a history of psychotic illness (schizophrenia, bipolar disorder, mania or hypomania, or other psychotic disturbances)

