# 13. Pharmacovigilance

# 13.1 General Definitions

The Medicines for Human Use (Clinical Trials) Regulations 2004 and Amended Regulations 2006 gives the following definitions:

Adverse Event (AE): any untoward medical occurrence in a subject to whom a medicinal product has been administered including occurrences which are not necessarily caused by or related to that product.

An AE can therefore be any unfavourable and unintended sign (Including an abnormal laboratory finding, for example), symptom or disease temporarily associated with the use of a medicinal product, whether or not considered to be related to the medicinal product.

Adverse Reaction (AR): any untoward and unintended response in a subject to an IMP which is related to any dose administered to that subject.

This definition implies a reasonable possibility of a causal relationship between the event and the IMP which is supported by facts, evidence or arguments to suggest a causal relationship. This definition includes medication errors and uses outside what is foreseen in the protocol (i.e. if an AR occurs as a result of a medication error), including misuse and abuse of the product.

Serious Adverse Event (SAE): any adverse event that:

- Results in death;
- o Is life-threatening;
- o Required hospitalisation or prolongation of existing hospitalisation;
- Results in persistent or significant disability or incapacity;
- o Consists of a congenital anomaly or birth defect.

These characteristics/consequences have to be considered at the time of the event. For example, regarding a life-threatening event, this refers to an event in which the subject was at risk of death at the time of event; it does not refer to an event which hypothetically might have caused death if it were more severe. Medical and scientific judgement must be exercised in deciding whether an event is 'serious' in accordance with these criteria.

**Serious Adverse Reaction (SAR)**: reference is made to the criterion of 'Seriousness' above in relation to SAE. Where an SAE is deemed to have been related to an IMP used within the trial, the event is termed as a SAR. (Any suspected transmission via a medicinal product of an infectious agent is also considered a serious adverse reaction.)

**Suspected Unexpected Serious Adverse Reaction (SUSAR)**: an adverse reaction, the nature and severity of which is not consistent with the pharmacovigilance reference copy of the mirtazapine SPC (Medreich Plc; PL number 21880/0053).

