### **13.3 BETTER-B Reporting Requirements**

Information about all events (AEs, ARs, SAEs, SARs and SUSARs), whether volunteered by the participant, discovered by investigator questioning or detected through physical examination, laboratory test or other investigation, must be collected and reported to the CTRU.

All SAEs, SARs and SUSARs (excepting those specified in this protocol as not requiring expedited reporting) must be reported immediately (and certainly **no later than 24 hours**) by the trial site team to the CTRU.

For each SAE/SAR or SUSAR the following information will be collected:

- event duration (start and end dates, if applicable)
- action taken
- outcome
- "key information":
  - full details in medical terms and case description (or signs / symptoms / diagnosis – i.e. adequate information describing the event)
  - o seriousness criteria

- causality (i.e. relatedness to mirtazapine / investigation), in the opinion of the investigator
- o whether the event would be considered expected or unexpected
- PI signature (or another clinically qualified member of the medical team authorised in the BETTER-B Authorised Personnel Log)

All events must be reviewed and assessed (for seriousness, causality and expectedness) by the PI, or another clinically qualified member of the medical team authorised in the BETTER-B Delegation Log. If an authorised medic is not available on the day the site team become aware of the event, initial reports without causality and expectedness must still be sent to the CTRU **within 24 hours** of the site becoming aware, and must be followed-up by medical assessment as soon as possible thereafter. Any outstanding "key information" (see above) must be reported within a further 24 hours. Subsequently, follow-up reports (detailing changes in condition) must be reported to the CTRU within 24 hours of the site becoming aware of a change relating to "key information", or at the time of the event resolving or, for all other data, when requested by the CTRU.

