#### 13.3.1 Reporting of Adverse Events (AEs) and Adverse Reactions (ARs)

All AEs occurring from randomisation up to 7 days after the last dose of trial treatment and all ARs occurring from the first trial treatment dose up to 7 days after the last dose of trial treatment must be recorded on the appropriate Trial Treatment Assessment CRF or Follow-up Assessment CRF, which will be posted to CTRU within 2 weeks of the assessment. These are not subject to expedited reporting to CTRU.

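### The list in section 13.2.1 of admissions that do not count as SAEs has no exception for suspected drug-related events, so a mixed-cause admission can miss SAR and SUSAR reporting

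*Protocol*

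**What the plan says.** Section 13.2.1 of the protocol names events that will not be treated as SAEs and so fall outside expedited reporting. Its first group is "Hospitalisation or admission into a hospice, nursing home or palliative care unit due to" a set of reasons. Three of these are disease items: expected deterioration of cancer; "Expected deterioration related to underlying lung disease diagnosis (COPD / ILD"); and, for heart failure, "Expected deterioration related to underlying chronic heart failure diagnosis (e.g. acute decompensation of heart failure, angina with or without raised troponins, cardiac arrhythmia". The section adds that "they will still need to be reported to CTRU along with other AEs". Nothing in or around the list says what happens when the investigator suspects the trial drug.

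Five other provisions bear on this:

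- **Causality (13.2.1, before the list, and 13.3).** Every AE and SAE is assessed for causality as though the participant were on mirtazapine. All events are assessed for seriousness, causality and expectedness by the PI or an authorised medic.
- **SAR definition (13.1).** "Where an SAE is deemed to have been related to an IMP used within the trial, the event is termed as a SAR".
- **Timing (13.3).** "All SAEs, SARs and SUSARs (excepting those specified in this protocol as not requiring expedited reporting) must be reported immediately", with 24 hours as the outer limit.
- **Timing (12.8 and 13.3.2).** SARs go to the CTRU within 24 hours of awareness. Neither section states an exception.
- **AE route (13.3.1).** Ordinary AEs and ARs are recorded on an assessment form, "which will be posted to CTRU within 2 weeks of the assessment".

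**The concern.** An admission need not have a single cause. Under 13.1 an adverse reaction requires only a reasonable possibility of a causal link, so an arrhythmia or a respiratory admission can fit expected deterioration of the underlying disease and also be possibly drug-related. For that mixed case the list gives one answer, that it is not an SAE, and does not ask about relatedness. Because the SAR class is built on the SAE class, the answer carries forward.

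At stake is the serious-event reporting of a blinded trial that has no separate DMEC (19.2). A related admission filed this way would have no SAE or SAR form (12.8), would not reach the Chief Investigator as a possible SUSAR (13.4), and would not appear in the SAE, SAR and SUSAR summary by arm (18.5.3).

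**Working it through.** The protocol gives no figure to reproduce. The check follows one hypothetical event through the text: a participant with heart failure is admitted with an arrhythmia, and the investigator thinks it fits the underlying disease but cannot rule out the trial drug.

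1. **Is it an SAE?** Under the general definition in 13.1, yes, because it required hospitalisation. Under the list in 13.2.1, no: it is an admission, it is due to deterioration of heart failure, and arrhythmia is a named example. The list is the more specific, trial-level rule and has no relatedness condition.

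2. **Is causality assessed?** Yes. Sections 13.2.1 and 13.3 require it for every event. Suppose the result is possibly related.

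3. **Does it become a SAR?** The sentence in 13.1 starts from an SAE judged related. Step 1 has removed the SAE label, so that sentence gives no route. The protocol does not say that a finding of relatedness restores the label.

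4. **If someone calls it a SAR anyway, is it expedited?** The sections differ. Section 13.3 attaches its exception to SAEs, SARs and SUSARs together, so a listed admission may be exempt even as a SAR. Sections 12.8 and 13.3.2 require SARs within 24 hours with no exception, but 13.3.2 refers back to 13.2 for its definitions, and the list sits in 13.2.

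5. **Does the important medical event rule catch it?** Not clearly. Sections 12.11 and 13.1 write that rule for events that may not lead to death or hospitalisation. The listed events are admissions.

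6. **What is the difference in timing?**
   - AE route: form posted up to 2 weeks, or 14 days, after the assessment (13.3.1; 12.15 gives the same interval for CRFs in general).
   - SAE or SAR route: 24 hours, or 1 day, after the site becomes aware (12.8, 13.3.2).
   - If the site becomes aware at the assessment itself, the difference is up to 14 − 1 = 13 days.

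7. **Where does it appear in the analysis?** It enters the toxicity summary by maximum CTCAE grade and arm in 18.5.3. It is not in the count of SAEs, SARs and SUSARs in the same section.

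8. **Who is covered?** The three disease items together span every diagnosis in inclusion criterion 2 (section 8.1). The arrhythmia and angina examples belong to the heart failure item only.

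**The case against.** The strongest reply is that the list is already tied to cause. It exempts an admission only when it is due to expected deterioration of the underlying disease, so one that the investigator attributes to the drug falls outside its words. Causality is assessed for every event as if on active drug. The definition of a SAR in 13.1 opens by referring to the seriousness criteria, and a SUSAR is defined there as an adverse reaction inconsistent with the SPC, without reference to the SAE label. The life-threatening and disability criteria are untouched. Exempt events are still reported, are tabulated by arm, and form part of the safety data that the TSC reviews unblinded.

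Most of this stands, and it rules out several stronger readings that a reader might infer:

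- **That the exemption applies whatever the suspected cause, or that a drug-caused admission can never become a SAR or SUSAR.** The wording about cause and the universal causality assessment contradict both. An admission attributed wholly to the drug is outside the list.
- **That notification slips to 21 days, by adding 7 days between contacts to the 14 days for posting.** The 24-hour clock also starts only at awareness, so waiting for a contact cannot be charged to one route alone. A site that hears of an admission between contacts might hold it longer as an AE, but the protocol does not say when sites hear of admissions.
- **That the list conflicts with the exclusion of "Patients with acute cardiac events within 3 months of randomisation (myocardial infarction, unstable angina pectoris, or significant cardiac conduction disturbance") in section 8.2.** That rule governs entry and is silent on reporting. Both can be followed.
- **That the exempt presentations are where mirtazapine harm would most likely appear.** Section 11.1.4 lists peripheral oedema, somnolence and sedation but does not link them to decompensation or respiratory decline. Section 5.2 describes antidepressants as having low risk of respiratory depression and mirtazapine as not associated with cardiovascular toxicity.

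The reply does not settle the mixed-cause event. Disease deterioration and possible relatedness are not mutually exclusive, and the protocol states no rule for when both apply. The mention of SARs and SUSARs in the 13.3 exception points towards exemption, since those are related events by definition.

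**Conclusion.** The concern holds as a gap in the reporting rules. Followed as written, an admission that fits expected deterioration and is also possibly drug-related can be handled as a non-expedited AE and left out of SAR and SUSAR review and counts. The sections pull in different directions, and two sites could classify the same event differently.

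For an affected event, the form may be posted up to 14 days after the assessment instead of being reported within 24 hours of awareness, and the event drops out of one of the two safety tabulations in 18.5.3. The number of such events cannot be derived: the protocol gives neither an admission rate nor the expected number of participants with heart failure.

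This rests on two assumptions: that a site applies the list once the disease description fits, and that no document outside the protocol supplies the missing condition. The heart failure item breaks off at an open bracket and runs into the next item. That may come from text extraction, and nothing here depends on it.

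**What to change.** - **13.2.1:** make the exemption conditional. A listed admission is exempt only if the investigator, assuming active drug, judges that there is no reasonable possibility that it is related to the IMP. Otherwise it is reported as a SAR and assessed for expectedness.
- **13.3:** limit the exception to listed admissions judged unrelated, and remove its application to SARs and SUSARs.
- **13.1, 12.8 and 13.3.2:** reconcile the SAR definition and the 24-hour rule with the two changes above, so that a related admission meeting a seriousness criterion follows one route throughout.

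The angina and arrhythmia examples need not be removed. With the relatedness condition in place, an admission judged to be disease-related only stays exempt, and deleting the examples would expedite events that no one suspects of being drug-related.

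The cost is a wording amendment and a few additional expedited reports in a trial of about 60 participants. The causality assessment on which it depends is already required for every event, so no new procedure is needed.

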#### BETTER-B

- Treatment which was elective or pre-planned, for a pre-existing condition not associated with any deterioration in condition, e.g. pre-planned hip replacement operation which does not lead to further complications;
- Any admission to hospital or other institution for general care where there was no deterioration in condition;
- Treatment on an emergency, outpatient basis for an event **not** fulfilling any of the definitions of serious as given above and not resulting in hospital admission.

#### Events classed as expected SAEs / SARs

Examples of events which will be classed as **expected** SAEs / SARs within this trial are given below. These will **not** be reportable as SUSARs on the trial, unless the severity of the event is considered to be unexpected.

This is not intended to be an exhaustive list, therefore when determining whether a SAE / SAR is expected or not, the pharmacovigilance reference copy of the mirtazapine SPC (Medreich Plc; PL number 21880/0053) must always be referred to.

Examples of expected SARs (related to mirtazapine):

- Increase in appetite
- Weight gain
- Somnolence
- Sedation
- Headache
- Dry mouth

All events should be reviewed and classified by the site PI, or another clinically qualified member of the medical team authorised in the BETTER-B Delegation Log.

#### 13.2.2 Suspected Unexpected Serious Adverse Reactions (SUSARs)

For general a definition of SUSARs, please see section 13.1 above.

SUSARs and will be subject to expedited reporting to the Medicines and Healthcare products Regulatory Authority (MHRA) and Research Ethics Committee (REC).

Events associated with placebo will usually not satisfy the criteria for a SUSAR and therefore expedited reporting. However, where SARs are thought to be associated with placebo (e.g. reaction due to excipient or impurity) the CTRU will report such cases to the CI for assessment of expectedness and, if appropriate, to the Sponsor for onward reporting to the MHRA and REC.

Routinely breaking the blind could compromise the integrity of the trial. For this reason blindbreaking will only take place where information about the participant's trial treatment is clearly necessary for the appropriate medical management of the participant. In all cases the Investigator would be expected to evaluate the causality and expectedness of SAEs/SARs as though the participant was receiving the active medication.

### **13.3 BETTER-B Reporting Requirements**

Information about all events (AEs, ARs, SAEs, SARs and SUSARs), whether volunteered by the participant, discovered by investigator questioning or detected through physical examination, laboratory test or other investigation, must be collected and reported to the CTRU.

All SAEs, SARs and SUSARs (excepting those specified in this protocol as not requiring expedited reporting) must be reported immediately (and certainly **no later than 24 hours**) by the trial site team to the CTRU.

For each SAE/SAR or SUSAR the following information will be collected:

- event duration (start and end dates, if applicable)
- action taken
- outcome
- "key information":
  - full details in medical terms and case description (or signs / symptoms / diagnosis – i.e. adequate information describing the event)
  - o seriousness criteria

- causality (i.e. relatedness to mirtazapine / investigation), in the opinion of the investigator
- o whether the event would be considered expected or unexpected
- PI signature (or another clinically qualified member of the medical team authorised in the BETTER-B Authorised Personnel Log)

All events must be reviewed and assessed (for seriousness, causality and expectedness) by the PI, or another clinically qualified member of the medical team authorised in the BETTER-B Delegation Log. If an authorised medic is not available on the day the site team become aware of the event, initial reports without causality and expectedness must still be sent to the CTRU **within 24 hours** of the site becoming aware, and must be followed-up by medical assessment as soon as possible thereafter. Any outstanding "key information" (see above) must be reported within a further 24 hours. Subsequently, follow-up reports (detailing changes in condition) must be reported to the CTRU within 24 hours of the site becoming aware of a change relating to "key information", or at the time of the event resolving or, for all other data, when requested by the CTRU.

#### 13.3.1 Reporting of Adverse Events (AEs) and Adverse Reactions (ARs)

All AEs occurring from randomisation up to 7 days after the last dose of trial treatment and all ARs occurring from the first trial treatment dose up to 7 days after the last dose of trial treatment must be recorded on the appropriate Trial Treatment Assessment CRF or Follow-up Assessment CRF, which will be posted to CTRU within 2 weeks of the assessment. These are not subject to expedited reporting to CTRU.

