# 11.3 Withdrawal of Treatment

In line with usual clinical care, cessation or alteration of regimens at any time will be at the discretion of attending clinicians or the participants themselves. All participants withdrawn from treatment or prescribed alternative treatment will still attend for follow-up assessments unless unwilling to do so and CRFs will continue to be completed.

The PI, or delegate should make every effort to ensure that the specific wishes of any participant who wishes to withdraw consent for further involvement in the trial are defined and documented using the Withdrawal CRF in order that the correct processes are followed by the CTRU and site following the withdrawal of consent.

It should be made clear to any participant specifically withdrawing consent for further data collection that data pertaining to safety will continue to be collected for regulatory reporting purposes and will be included in any safety analysis. In addition it is suggested that the participant is made aware of the fact that if any significant new information becomes available in regard to the treatment they have received in the trial it may be necessary to contact them in the future.

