# 12.10 Deaths

All deaths occurring from the date of randomisation to 7 days after the participant has completed trial treatment must be recorded on the Notification of Death CRF and sent to the CTRU **within 7 days** of the site becoming aware of the death (please see section 21 for details of acceptable methods of transfer).

At the end of the trial, sites will be contacted to provide data on any subsequent deaths and survival data.

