#### 13.3.2 Expedited Reporting of Serious Adverse Events (SAEs), Serious Adverse Reactions (SARs) and Suspected Unexpected Serious Adverse Reactions (SUSARs)

All SAEs, SARs and SUSARs (see section 13.2 above for definitions) must be recorded on the appropriate CRF (SAE or SAR) and reported to the CTRU **within 24 hours** of the local research team site staff becoming aware of the event (this includes participants who have withdrawn consent for data collection, see section 11.3). Once all resulting queries have been resolved, the original wet-ink CRF will be posted to the CTRU and a copy retained at site.

Please ensure that only one event is reported on each SAE and SAR CRF (details of multiple symptoms should be listed if they relate to the same event).

SAEs, SARs and SUSARs must be reported in an expedited manner (within 24 hours of the research team becoming aware) during the active monitoring period, which is defined as occurring from randomisation (for SAEs) or from the first trial treatment dose (for SARs and SUSARs) up to 7 days after the last dose of trial treatment.

If sites become aware of any SARs or SUSARs occurring after this active monitoring period, these must still be reported in an expedited manner **up until 90 days after the End of Trial**.

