# 13.4 Responsibilities

#### **Principal Investigator:**

- 1. Checking for AEs and ARs when participants attend for treatment / follow-up (this may be delegated to an appropriate member of the trial team) and ensuring that AEs and ARs are recorded and reported to the CTRU in line with the requirements of the protocol.
- 2. Checking for SAEs when participants attend for treatment / follow-up (this may be delegated to an appropriate member of the trial team).
- 3. Using medical judgement in assigning seriousness, causality and expectedness using the version of the pharmacovigilance reference copy of the mirtazapine SPC (Medreich Plc; PL number 21880/0053).
- 4. Ensuring that all SAEs (occurring up to 7 days after a participant's last trial treatment dose) and SARs, including SUSARs (occurring up to 90 days after the End of Trial) are recorded and reported to the CTRU within 24 hours of becoming aware of the event and provide further follow-up information as soon as available. Ensuring that SAEs and SARs (including SUSARs) are chased with CTRU if a record of receipt is not received within 2 working days of initial reporting.
- 5. Ensuring that SAEs are reported to local committees in line with local arrangements.

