#### 16.2.3 Safety and Toxicity

- Adverse events, using the Common Terminology Criteria for Adverse Events (CTCAE) categorisation (v4)  as reported at the assessment visits/calls for days 7, 14, 21 and 28.
- Safety will be reported based on the occurrence of SAEs, SARs and SUSARs.
- Australia-modified Karnofsky Performance Status (AKPS) and modified Medical Research Council (mMRC) dyspnoea scale at the assessment visits for days 14 and 28.

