#### 18.5.3 Safety and Toxicity

The number of SAEs, SARs and SUSARs will be summarised descriptively by arm, by causality, seriousness, and body system.

The proportion of participants experiencing each toxicity will be summarised by maximum NCI CTCAE grade experienced over 28 days, by treatment arm.

The change in AKPS and mMRC from baseline to day 14 and 28 will be summarised.

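### Section 13 requires AE and SAE recording only to 7 days after the last dose, while section 12 collects toxicity to day 28 and the toxicity table covers a fixed 28 days, so the period observed is unclear for participants who stop before day 21

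*Protocol*

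**What the plan says.** **Required recording (section 13).** AEs count from randomisation and ARs from first dose. Under 13.3.1 both are required "up to 7 days after the last dose of trial treatment must be recorded on the appropriate Trial Treatment Assessment CRF" or the Follow-up form. The active monitoring period for serious events in 13.3.2 has the same end ("for SARs and SUSARs) up to 7 days after the last dose of trial treatment"). The Principal Investigator duties in 13.4 repeat it for "all SAEs (occurring up to 7 days after" a participant's last dose.

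**Continued follow-up (sections 11 and 12).** Section 11.3 says "All participants withdrawn from treatment or prescribed alternative treatment will still attend for follow-up assessments" unless unwilling, with CRFs still completed. Table 1 schedules a toxicity assessment at every contact. The day 28 visit (12.5.4) collects any event since the day 21 call, and 12.8 puts all AEs and ARs in the trial on the weekly and follow-up forms. None of these mentions a last-dose limit.

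**Endpoint and analysis.** Section 16.2.3 defines the endpoint by CTCAE category "as reported at the assessment visits/calls for days 7, 14, 21 and 28". Section 18.5.3 gives the proportion with each toxicity "summarised by maximum NCI CTCAE grade experienced over 28 days, by treatment arm". The safety population (18.2) is everyone who took at least one dose.

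**Exceptions.** The death form in 12.10 covers "All deaths occurring from the date of randomisation to 7 days after the participant has completed trial treatment", but sites are asked for later deaths and survival at the end of the trial. Section 13.3.2 also provides for late serious reactions: "If sites become aware of any SARs or SUSARs occurring after this active monitoring period", they are still reported, up to 90 days after End of Trial.

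**The concern.** A participant who takes the last dose on day 5 passes the section 13 limit on day 12 but stays in the denominator of a 28-day table. Section 13 does not require non-serious events, or SAEs judged unrelated, from the remaining 16 days; section 12 collects them at the day 14, 21 and 28 contacts. One site can stop recording at last dose + 7 and another can continue to day 28, each with protocol text behind it. The table would then mix two observation periods.

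This matters for comparing the arms. Section 5.4 justifies a placebo control partly because these patients have adverse events from their underlying disease, so harm is to be judged by contrast between arms and not only by attribution of single events. The events left optional are the ones that contrast needs. If stopping is related to treatment, the arm with more stopping could look safer than it is.

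**Working it through.** The protocol gives no figure for this, so there is none to reproduce. The check has two parts.

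**1. Days at issue.** A last dose on day s closes the section 13 window on day s + 7. The days of the 28-day period outside it are max(0, 28 − (s + 7)) = max(0, 21 − s).

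| Last dose on day | Window closes on day | Days of the 28 outside it |
|---|---|---|
| 1 | 8 | 20 |
| 5 | 12 | 16 |
| 7 | 14 | 14 |
| 14 | 21 | 7 |
| 20 | 27 | 1 |
| 21 or later | 28 or later | 0 |

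Only a last dose before day 21 matters. If stop days are uniform over days 1 to 27 (assumption), 20/27 = 74% of stoppers are affected, and the mean number of days at issue per stopper is (20 + 19 + … + 1)/27 = 210/27 = 7.8.

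**2. Effect on the table if every site applied the section 13 limit.**

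Inputs from the protocol: 30 participants per arm and expected attrition of about 20% overall (section 17). Assumptions: stopping of 30% v 10%, which averages to that 20%; a true 28-day risk p = 0.40 in both arms; a constant hazard.

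- Hazard: h = −ln(1 − 0.40)/28 = 0.01824 per day.
- Recorded risk for a stopper on day s: 1 − exp(−h × min(28, s + 7)). Averaged over the assumed stop days this is m.
- Recorded proportion in an arm with stopping rate q: (1 − q) × 0.40 + q × m.

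| Stop days (uniform) | m | 30% stopping | 10% stopping | False difference |
|---|---|---|---|---|
| 1 to 27 | 0.303 | 0.7 × 0.40 + 0.3 × 0.303 = 37.1% | 0.9 × 0.40 + 0.1 × 0.303 = 39.0% | −1.9 points |
| 1 to 14 | 0.230 | 34.9% | 38.3% | −3.4 points |
| 1 to 7 | 0.181 | 33.4% | 37.8% | −4.4 points |

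In participants, that is 30 × 0.019 = 0.6 to 30 × 0.044 = 1.3 of 30. Over p = 0.20 to 0.60, and stopping from 30% v 10% to 40% v 10%, the false difference runs from −1.0 to −9.0 points (0.3 to 2.7 of 30). With 20% stopping in both arms it is 0: each arm is under-counted by the same amount.

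If collection ran to the later of day 28 and last dose + 7, m would equal 0.40 and both arms would show the true 12.0 of 30.

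**The case against.** The strongest reply is that the protocol, read as a whole, already collects toxicity to day 28. Section 13.3 opens by requiring information on all events. Section 13.4 has the investigator check for AEs, ARs and SAEs at treatment and follow-up attendances. Sections 11.3, 12.5.4 and 12.8 carry no last-dose limit, and 13.3.1 sets a minimum without forbidding later entries. This stands to the extent that loss of data is not certain. It does not settle the matter, because 13.3.1, 13.3.2 and 13.4 state an explicit end that the other sections do not repeat or override, and 12.6 does not say whether the 7-day call replaces or adds to the remaining contacts.

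A reader might infer more: that early stoppers leave harm collection, that deaths before day 28 are missed, and that the table is biased in favour of the arm with more stopping. The documents do not support this. Section 12.10 asks sites for subsequent deaths and survival, so only the prompt notification form ends early. Late SARs and SUSARs known to the site stay reportable. The protocol gives no stopping rate by arm. A toxicity that itself causes stopping is already counted. A constant hazard more than a week after the last dose probably overstates missed drug reactions.

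It is also fair to say that treatment plus 7 days is a defensible window for describing adverse reactions, that the analysis is descriptive, and that 6.3.2 and 16.2.1 keep toxicity out of the decision to proceed. These points limit the consequence. They do not align the window with the 28-day table.

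**Conclusion.** The inconsistency is real and narrow. It affects participants whose last dose is before day 21, and non-serious events and SAEs judged unrelated that occur between last dose + 7 and day 28. Sites may record different periods for them, while the denominator and the 28-day label stay fixed.

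A between-arm under-count is possible but not established. It needs sites to apply the section 13 limit and stopping to differ by arm. Under the assumed 30% v 10% stopping and equal 40% risk it is about 2 to 4 percentage points, or roughly one participant in 30; under equal stopping it is zero. This is a cheap improvement to a descriptive safety table, not a threat to the primary recruitment endpoint.

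**What to change.** Reconcile 13.3.1, 13.3.2 and 13.4 with 11.3, 12.5.4, 12.8 and 18.5.3. End AE and SAE collection at the later of day 28 after first dose and 7 days after the last dose, for participants still being followed. In 12.6, state that for early stoppers the 7-day call is additional to the remaining scheduled contacts. Section 12.10 needs no change.

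The cost is protocol wording, since 11.3 and Table 1 already schedule the contacts. The downside is a few extra off-treatment AE and SAE records, including some SAE forms under the 24-hour rule. Recording days since last dose lets these be flagged and, if wanted, tabulated separately.
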